## Detailed Protocol

### Development of Ingestible Biosensors to Enhance PrEP Adherence in Substance Users (PrEPsteps)

Treatment as usual	

• Return unused digital pills from prior 60-day period (onsite)

• Review of adherence data, discussion surrounding nonadherent events (remote or onsite)

• DBS testing to confirm PrEP adherence (onsite)

• Urine drugs of abuse screen (onsite)

--------------------	--

[figure not shown]
Study Visit 6: Procedures for this visit will be conducted onsite at Fenway Health, or partially remote, if necessary, in response to COVID-19. This visit will take place 3 months after study visit 5 (6 months post randomization). We will conduct a DBS to assess PrEP adherence. We will ask participants to complete a brief quantitative assessment (see attached *PrEPsteps\_Quantitative Assessment\_Visits 5+6*), via REDCap.

In the event that Study Visit 6 is conducted in a partially remote format, we will connect with participants via Zoom and ask them to complete a brief quantitative assessment (see attached *PrEPsteps\_Quantitative Assessment\_Visits 5+6*), which will be sent via email or REDCap survey link. For the onsite portion of this visit, we will conduct a DBS to assess PrEP adherence.

See study schematic below for a breakdown of Aims 2 and 3 study procedures:

## PrEPsteps Aim 2 Study Flow

### Onsite & Remote Procedures

## Detailed Protocol

### Development of Ingestible Biosensors to Enhance PrEP Adherence in Substance Users (PrEPsteps)

At the conclusion of this study, we will provide the following avenues in which study participants can continue to access PrEP outside of the study: First, participants can return to their primary care provider and ask them to prescribe PrEP, second, we can refer participants to a provider at Fenway Health to prescribe PrEP and finally, participants can access PrEP through the Brigham and Women's Infectious Disease Clinic.

**Remuneration:** Participants will be remunerated via ClinCards using the following schedule. Participants will only receive compensation for completed study visits. Participants who enrolled prior to the start of the PrEPsteps supplement in September 2022, and who elect to complete the additional questions added to the baseline quantitative assessment, will be compensated an additional \$20.

Study Visit	Compensation
Screening Visit	\$20
Study Visit 1	\$20
Study Visit 2	\$30
Study Visit 3	\$30
Study Visit 4	\$30
Study Visit 5	\$40
Study Visit 6	\$50
Additional Supplement Questions (if applicable)	\$20
Total	\$240

**Participant Contact:** We will contact participants via text message at described times after study visits (see *PrEPsteps Study Messages\_Participant Only*). Additionally, if participants do not respond to text messages (e.g., technology check-ins at days 2, 5, 7, 16, 19, 21), we will contact them via phone, and/or email. We will also contact participants to remind them of upcoming study visits via phone, Nomi text message, patient portal, and/or email. Upon participant request, we will inform them of the results of the urine drugs of abuse screen at study visits 3 and 5 via phone or in-person. As part of the PrEPsteps supplement, questions were added to the baseline quantitative assessment (*PrEPsteps\_Quantitative Assessment\_Visit 1*). The study team will contact participants via phone who completed the Study Visit 1 baseline quantitative assessment prior to the addition of the PrEPsteps supplement questions (in September 2022) to inquire about their interest in completing the additional supplement questions.

**Standard Operating Procedures for Nonadherence:** The digital pill technology has the potential to report real time PrEP adherence data during the course of this study. Recognizing standard medical care does not include daily reminders around PrEP adherence, we have developed a standard operating procedure to surround nonadherence/non-detection of digital pill ingestion during the study. Communication surrounding nonadherence is detailed in a separate document (SOP\_nonadherence).

**Drug Procurement:** Digital pills are procured from ARx Pharmacy (our collaborating pharmacy). Once participants sign informed consent during the Screening Visit, and we have confirmed qualifying laboratory work and eligibility, we will fax a Patient Prescription and Enrollment Form to ARx. This order form will contain the following information, as required by ARx per drug dispensing requirements: (1) participant's name; (2) participant's date of birth; (3) participant's study ID number; (4) participant's phone number; (5) participant's mailing address; (6) participant's drug allergies and current medications (if applicable); (7)

## Detailed Protocol

### Development of Ingestible Biosensors to Enhance PrEP Adherence in Substance Users (PrEPsteps)

participant's anticipated start date; (8) target drug delivery date; and (9) delivery information for pharmacist at Fenway Pharmacy. Following receipt of the Patient Prescription and Enrollment Form, ARx will mail 21 digital Truvada pills to cover the 14-day run in period (including 7 digital pills for any operational delays). Upon determination that the participant is eligible to continue in the study, the study team will fax a second Patient Prescription and Enrollment Form to ARx (same order form as for initial run-in period). ARx will then mail 90 digital pills (three 30-day supplies) to the Fenway Pharmacy. Confirmation of all shipment receipt will be documented in the PrEPSteps Pharmacy SOP binder. At Study Visits 1, 2, and 3, we will complete a Prescription Card that study staff will bring to the Fenway Pharmacy, who will sign out drug to us. If participants no-show during their study visit, we will return and sign back in drug to the Fenway Pharmacy. Leftover drug (during study visits, or in the case of lost to follow up) will be kept at Fenway. Pharmacy labels will be scratched off and destroyed to protect participant privacy prior to return to our industry collaborators at a time to be determined.

**Study Visit Scheduling:** We will schedule study visits as close to 30 days apart as possible. Recognizing that participants may have scheduling conflicts, we will seek to schedule participants for study visits within 7 days prior to the 30-day mark in order to prevent participants from running out of digital PrEP pills. For participants who have completed the screening visits (Study Visits 1 and 2), we will continue to contact them if they are eligible for the study in order to progress to Study Visit 3. We will review participants who are lost to follow up at this stage to determine if continued attempts to contact them are warranted. All remote portions of study visits (via Zoom) will be scheduled as close in proximity as possible to the in-person portions of those visits.

**Risk Assessments:** A licensed clinician will be onsite during all study visits where the quantitative assessment component is completed in-person. If a participant answers "nearly every day" to question #9 on the PHQ9, indicating suicidality, this will trigger a safety evaluation by a licensed clinician (e.g., [name]) before the participant is released. The clinician will review the results of the assessment with the participant, evaluate their safety and risk of harm, and make clinical referrals to Brigham and Women's Hospital if needed. In the unlikely event that the PI cannot be reached, another licensed clinician will conduct the safety evaluation. The participant's primary treating physician will be notified of any clinical referrals made as a result of this evaluation.

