## **II. Specific Aims**

***Aim 1:*** *To inform the specification of the PrEPsteps adherence intervention with participant-generated content solicited through five focus groups. We will solicit feedback from the focus group participants on all the components of the PrEPsteps intervention delivery content and platform.*

***Aim 2:*** *To test, through a pilot randomized controlled trial (N=30x2), the feasibility, acceptability and potential for an effect of PrEPsteps on PrEP adherence, compared to treatment as usual (TAU) in HIV seronegative MSM with non-alcohol substance use who are initiating or continuing PrEP.*

***Aim 3:*** *To assess the acceptability of the PrEPsteps intervention components (and the digital pill) through qualitative exit interviews with those randomized to the PrEPsteps condition.*

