**Study Visit 2:** Procedures for this visit will be conducted onsite at Fenway Health, or partially remote, if necessary, in response to COVID-19. This visit will take place 2 weeks after Study Visit 1. We will contact participants on day 7 to remind participants of their appointment. Participants will be randomized into the control arm (treatment as usual with digital pills to measure adherence) or the intervention arm (PrEPsteps). Randomization will occur via a predetermined schema using REDCap. We will review the previous 2 weeks of adherence data and reconcile discordant or nonadherent events with participants. At this study visit and subsequent study visits, participants will have the option of viewing the original digital pill training videos used in Study Visit 1 as a refresher course for technology training if they desire. Participants will return any unused digital pills from the prior 14-day period (to be counted by study staff), and will additionally undergo a blood draw for dried blood spot (DBS) testing for tenofovir diphosphate (to measure adherence and compare DBS against the digital pill). For all participants, a 30-day supply of Truvada digital pills will be dispensed at this study visit. We will contact participants via text message on days 16, 19, 21 to ensure technology is functioning. *This contact schema (i.e., reminder messages for study visit) will remain the same for each subsequent visit.*

In the event that Study Visit 2 is conducted in a partially remote format, we will randomize the participant, review the previous 2 weeks of adherence data, and provide the link to the digital pill training videos during the virtual (Zoom) portion of this visit. All remaining study visit procedures will be conducted during the onsite portion of this visit. If necessary, the 30-day supply of digital pills may be mailed to participants if they are unable to attend the in-person portion of the visit due to COVID-19.

Arm	Study Visit 2 Procedures
-----	--------------------------

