## VII. Biostatistical Analysis

**Aim 1:** We will conduct qualitative analysis on individual interviews in aim 1 to elucidate themes of technology acceptance, design, and optimal timing and delivery of messaging.

**Aim 2:** We will calculate descriptive statistics regarding the degree of adherence collected from the digital pill. We will also calculate the accuracy of the digital pill in comparison to pill counts and validate ingestion data compared to DBS. We additionally will report overall percent adherence and measure the association between percent adherence and PrEPSteps. Additionally we will report weeks of adherence ( $>4$  doses a week) and measure the association between weeks of adherence and the use of PrEPSteps. Because this is a pilot, proof-of-concept study, we will not be powered to determine the degree of adherence the use of a digital pill alone confers upon study participants.

**Aim 3:** We will conduct an applied thematic analysis on all recorded interviews using NVivo 12.

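### The Study Visit Scheduling text places an eligibility condition and a discretionary follow-up decision after randomisation, in conflict with the Study Visit 2 and 3 procedures; the passages need reconciling (moderate).

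*Combined protocol and SAP*

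**What the plan says.** The protocol text appears twice in the combined document, and both copies read alike on this point.

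- **Section VI, Study Visit 2** (two weeks after Visit 1): "Participants will be randomized into the control arm" or the PrEPsteps arm, and "Randomization will occur via a predetermined schema using REDCap". In the partially remote format, randomisation is listed ahead of the review of run-in adherence data.
- **Section VI, Study Visit 3:** the visit falls 30 days after randomisation.
- **Section VI, Study Visit Scheduling:** for participants who have "completed the screening visits (Study Visits 1 and 2"), the plan is that "we will continue to contact them if they are eligible for the study in order to progress to Study Visit 3". The team will then review those lost to follow-up at this stage "to determine if continued attempts to contact them are warranted". No criteria and no number of attempts are given.
- **Section VI, Drug Procurement:** the second pill order follows a determination that the participant may continue. Its criteria, and its timing relative to allocation, are not stated.
- **Section VII, Aim 2:** no analysis population is defined, and there is no rule for randomised participants who have no later data.

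**The concern.** On the current visit numbering, everyone who has completed Visit 2 has been randomised. A condition that they be eligible, and a judgement about whether they are worth pursuing, then operate on randomised people. If the staff making those decisions know the arm and the adherence record to date, the decisions could be related to both. Poor adherers could be followed less completely in one arm than in the other, and the comparison of adherence would partly reflect who was kept in contact.

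An as-randomised analysis, even if stated, could not recover Visit 3 and later data that were never collected. Pilot status does not remove the issue, because Aim 2 looks for a potential effect on adherence in a "pilot randomized controlled trial (N=30x2"), and retention is part of feasibility.

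**Working it through.** **1. The plan's own figures.** They agree: 30 × 2 = 60 randomised; 14 + 7 = 21 run-in pills; 30 (Visit 2) + 60 (Visit 3) = 90, the size of the second pill order. No stated figure is wrong. The issue is the order of events.

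**2. Order of events under the current numbering.**

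| Step | Where stated | Relative to allocation |
|---|---|---|
| Listed eligibility and laboratory work confirmed | Screening Visit; Drug Procurement | Before |
| Run-in starts | Study Visit 1 | Before |
| Allocation in REDCap | Study Visit 2 | Allocation |
| Decision to continue, then 90-pill order | Drug Procurement | Not stated |
| Contact towards Visit 3 conditional on eligibility | Study Visit Scheduling | After |
| Decision whether to pursue those lost | Study Visit Scheduling | After |
| Study Visit 3 | Study Visit 3 | 30 days after |

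Two rows fall after allocation, and one is undefined.

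**3. When the continuation decision was probably meant to occur.** The 90 pills go to the Fenway Pharmacy and include the 30 dispensed at Visit 2. The order, and the decision that triggers it, would therefore normally precede or coincide with Visit 2. This is an inference; the text does not say it.

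**4. Whether the numbering is left over.** The Screening Visit plus Visits 1 to 6 makes the seven visits that Section VI announces. If Screening is counted as Visit 1, the current Visit 2 becomes Visit 3. That count would explain two other mismatches:
- The intervention description places the LifeSteps session at Visit 3, but the procedure table places it at Visit 2.
- Section XI places dried blood spots at Visits 3 and 4, but Section VI takes them at Visits 2 and 3, and Visit 4 is entirely remote.

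On that count the eligibility condition falls before allocation. Against it, Drug Procurement, directly above the scheduling text, has drug signed out at Visits 1, 2 and 3, which is the current numbering. The documents do not settle the matter.

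**5. What staff know.** No blinding is described. Staff programme LifeSteps responses in the PrEPsteps arm only (Visit 2 table) and review adherence data with participants. Section XI has investigators conduct quality reviews by arm. Knowledge of arm is inferred from these tasks.

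**6. What can be lost.** A participant not brought to Visit 3 and not sent the refill misses 60 of the 90 pill-days after randomisation, and may miss the dried blood spots at Visits 3, 5 and 6. Ingestions from the 30 pills given at Visit 2 that have already been transmitted are kept.

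**7. Size, illustration only.** Assume that retained participants average 75% adherence, dropped ones 40%, a fraction f is dropped from one arm only, and there is no true effect.

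Bias = 75 − [(1 − f) × 75 + f × 40] = 35f

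- f = 0.10 (3 of 30): 3.5 points
- f = 0.15: 5.25 points
- f = 0.20 (6 of 30): 7.0 points

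If both arms lose fractions f₁ and f₂ on the same terms, the net bias is 35(f₁ − f₂), which is zero when they are equal.

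A simulation with no true effect (30 per arm, standard normal outcome, two-sided t-test at 0.05, 20,000 runs, removal from one arm only; all assumed) gave:

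| Removed from one arm | Bias (SD) | False-positive rate |
|---|---|---|
| None | 0 | 4.8% |
| Lowest 1 | 0.07 | 6.2% |
| Lowest 3 | 0.18 | 12.4% |
| Lowest 6 | 0.34 | 27.6% |
| 3 to 6, removal correlated 0.3 to 0.5 with adherence | 0.05 to 0.17 | 5.3% to 9.5% |
| 3 or 6 at random | none expected | about 5% |

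Removing exactly the lowest adherers is the extreme case. The moderate-correlation row is less severe.

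**The case against.** The strongest case on the other side is that this is a numbering slip with little behind it. Listed eligibility is confirmed before Visit 1, the pill order points to a continuation decision no later than Visit 2, and other passages fit a count in which Screening is Visit 1. The sentence on pursuit concerns people already lost, and asks only whether more attempts are worthwhile. Phone and email contact for non-responders is described without distinction of arm, and the data safety monitoring board reviews retention. All of this stands, and it lowers the severity. It does not remove the gap: the alternative numbering is not proven, neither the board nor the contact text sets a follow-up rule, and Section VII does not say who is analysed.

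A reader might infer more: that eligibility as a whole is decided after randomisation, or that unblinded staff may drop randomised participants from the trial so that comparability is lost. The documents do not support that. The listed criteria are applied earlier, no text withdraws a reachable participant or excludes anyone from analysis, and no text varies contact effort by arm. What falls after Visit 2 is a second, undefined condition and an open judgement about people already lost.

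**Conclusion.** The concern holds as a conflict between passages with an avoidable risk attached; severity is moderate. The Study Visit Scheduling text cannot be reconciled with the Study Visit 2 and 3 procedures under the current numbering. Followed literally, it permits selective loss of follow-up after randomisation. That this would happen, or would differ by arm, is not established.

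The 3.5 to 7.0 points and the simulated rates only scale the risk. They rest on assumed adherence levels, assumed fractions lost, and loss from one arm only; none is a document figure. The conclusion also rests on the inference that the staff concerned know the arm. In a pilot of 30 per arm with no power calculation, this does not amount to a defect that invalidates the design, but lost follow-up cannot be restored later.

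**What to change.** Make these changes in both copies of the text:

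1. Reconcile the visit numbering across Study Visit Scheduling, the LifeSteps description and message table, the dosing-window text under Study Visit 1, and the dried blood spot visits in Section XI.
2. State that any run-in or continuation eligibility decision is final before the REDCap allocation at Visit 2 is released, and give its criteria.
3. For randomised participants, remove the eligibility condition on contact and the description of Visit 2 as screening.
4. Replace the case-by-case judgement with one fixed rule for contact attempts, the same in both arms.
5. In Section VII, state that all randomised participants are followed and analysed in the assigned arm, and that losses after randomisation are reported by arm with reasons.

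The cost is a few sentences of wording and some extra contact attempts. Sample size and assessments do not change.

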## VII. Biostatistical Analysis

**Aim 1:** We will conduct qualitative analysis on individual interviews in aim 1 to elucidate themes of technology acceptance, design, and optimal timing and delivery of messaging.

**Aim 2:** We will calculate descriptive statistics regarding the degree of adherence collected from the digital pill. We will also calculate the accuracy of the digital pill in comparison to pill counts and validate ingestion data compared to DBS. We additionally will report overall percent adherence and measure the association between percent adherence and PrEPSteps. Additionally we will report weeks of adherence ( $>4$  doses a week) and measure the association between weeks of adherence and the use of PrEPSteps. Because this is a pilot, proof-of-concept study, we will not be powered to determine the degree of adherence the use of a digital pill alone confers upon study participants.

**Aim 3:** We will conduct an applied thematic analysis on all recorded interviews using NVivo 12.

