## **XI. Data Monitoring and Quality Assurance**

## Detailed Protocol

### Development of Ingestible Biosensors to Enhance PrEP Adherence in Substance Users (PrEPsteps)

We will review and monitor data from PrEPsteps for each study participant. At each study visit, participants will undergo pill counts to correlate adherence data from PrEPsteps, and calculate the accuracy of the digital pill to measure PrEP adherence. Any discrepancies between the digital pill and pill counts will be addressed in real time at each study visit with the participant. For each participant, we will also review signaling from the digital pill to the Reader with our industry collaborator (etectRx) to ensure there are no errors in data transmission contribution to missed adherence events. If errors occur as a result of data transmission, we will correct the participant's adherence data, and convey these changes to participants' PCP via Mimecast secure email. We will additionally obtain dried blood spot testing at study visits 3 and 4 to confirm adherence (see section V. study procedures)

Recorded interviews: Audio-recorded interviews (Aim 1 and 3) will be transcribed using a HIPAA compliant transcription service (Landmark transcription), and scrubbed of identifiers

Aim 2 QA review: Study investigators will conduct QA review of baseline adherence data after the first 10 participants are enrolled. Additionally, we will review adherence data and interactions with PrEPsteps after the first 10 participants randomize to PrEPsteps. We will similarly conduct QA review after the first 10 participants randomize to treatment as usual. We will continue to conduct subsequent QA reviews in increments of 10 participants enrolled in each arm to ensure fidelity of the study data.

**Data Safety Monitoring Board (DSMB):** Three investigators who are external to the study and external to [name] mentoring team as defined by his NIH K23 award with expertise in PrEP, non-alcohol substance use disorder, technology security and behavioral interventions, will comprise a DSMB for Aim 2 (pilot randomized controlled trial) of the research plan. The DSMB will convene annually during Aim 2. Additionally, the DSMB will meet when N=30 study participants are enrolled in Aim 2. They will review the data, and any potential study related adverse events prior to approving the continuation of recruitment. The responsibilities of the DSMB will include:

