- Reviewing the research protocol, consent form, and plans for DSMB.
- Evaluating the progress of the pilot randomized controlled trial: recruitment, retention, data quality, site performance, adverse events.
- Protection of participant safety
- Making recommendations to [name] and the Fenway Institute IRB regarding continuation, termination or modification of the study depending on benefits or adverse events.
- Ensuring the confidentiality of study data.
- Reviewing adverse events.
- Providing annual written reports to [name], and NIH regarding safety concerns, continuation or modification of the research plan.

We will additionally comply with all Fenway regulations regarding reporting of adverse events and ensuring data quality.

**Data Tracking:** Ingestion data will be automatically logged into the web interface hosted by ectectRx with a date/time stamp to ensure accurate record keeping of all data and linking to the results. All data will be securely accessed at Fenway Health.

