**Data Entry Process:** Protected health information, including study participant demographics, non-alcohol substance use disorder history, and HIV risk factors will be collected by [name] and the research assistant and entered into REDCap, a secure web application being used for data storage and management. A separate spreadsheet of study participant contact information and a technology log including participant mobile phone number, electronic mail (email) address, identifiers of the Receiver, study smartphone and a log of dispensed digital pills will also be maintained by [name] and the RA. All logs will be stored behind TFI firewall and password protected. Each variable with missing data (such as an interruption between smartphone and sensor) will be identified and a placeholder (“<<-99>>”) entered to connote a missing value. Data from the digital pill is recorded on the ectectRx interface and automatically transferred via a HIPAA-compliant secure link to the adherence interface (NOMI). Ingestion data may potentially require editing if there are transmission failures, errors from the reader device, or manually recorded data from study participants. All of these potential edits will be identified by ectectRx in collaboration with the study team. Edits to data will be agreed upon by both parties and approved by the PI. An audit trail of all potential edits will be maintained. We will additionally comply with Fenway regulations regarding reporting of adverse events and ensuring data quality. Landmark Associates Inc, an external company, will be contracted to transcribe audio-taped exit interviews.

**Data Storage:** Raw ingestion data, transcripts from this study and self-report questionnaires will not be made publicly available. De-identified data may be shared with NIH who is funding the study, as well as industry collaborators ectectRx and NOMI. For future investigations that use de-identified participant data, we will submit IRB protocols detailing the use of this data. Mass General Brigham Dropbox is being used for file storage in the study.

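### The Aim 2 arm comparison in Section VII makes no use of the 14-day run-in digital-pill adherence; adjusting for it would probably narrow the confidence interval at almost no cost

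*Combined protocol and SAP*

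**What the plan says.** Section II sets Aim 2 as a pilot randomised trial of 30 per arm, testing "the feasibility, acceptability and potential for an effect of PrEPsteps on PrEP adherence, compared to treatment as usual (TAU". For the adherence comparison, Section VII states "We additionally will report overall percent adherence and measure the association between percent adherence and PrEPSteps", and that the investigators will "measure the association between weeks of adherence and the use of PrEPSteps". It names no model, covariate or outcome window. The text is the same in both copies in the combined file.

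The trial collects a baseline on the outcome scale. Under Section VI, Study Visit 1, participants take a first digital pill under observation and then use digital pills until Study Visit 2 two weeks later. Drug Procurement calls this a run-in: "ARx will mail 21 digital Truvada pills to cover the 14-day run in period". Randomisation comes at Study Visit 2: "Participants will be randomized into the control arm (treatment as usual with digital pills to measure adherence) or the intervention arm (PrEPsteps". It follows a predetermined REDCap schema, and no stratification is stated. The only planned use of what Section XI calls baseline adherence is quality assurance: "Study investigators will conduct QA review of baseline adherence data after the first 10 participants are enrolled".

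Two data-handling statements in Section XI bear on how a covariate could be built. Under Data Tracking, "Ingestion data will be automatically logged into the web interface hosted by ectectRx with a date/time stamp". Under Data Entry Process, ingestion data may be edited after transmission or reader failures: "Edits to data will be agreed upon by both parties and approved by the PI".

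**The concern.** Run-in adherence is measured before allocation, on the same device and scale as the outcome, and comes from data already collected. It is the natural covariate for the arm comparison. A pilot of 60 that looks for a possible effect has, as its main quantitative product, an arm difference with its interval. Anything that narrows that interval without new data is worth having.

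There is also a matter of pre-specification. With 30 per arm and no stated stratification, a chance difference in run-in adherence is quite possible. If the plan is silent, the choice to adjust could be made after the results are seen.

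**Working it through.** **Inputs.** From the documents: 30 per arm (Section II); 14-day run-in before randomisation and 90 pills after it (Section VI, Drug Procurement). Not given: the correlation r between run-in and follow-up adherence, the mean and SD of adherence, alpha. I assume a two-sided 95% interval and a range of r. The plan has no precision figure to reproduce.

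**Step 1: effect on interval width.** Adjustment multiplies the residual variance by 1 − r². The covariate costs one degree of freedom (t with 57 instead of 58) and, on average, a factor 1 + 1/56 for chance imbalance in the covariate. So

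width ratio = (t57/t58) × √[(1 − r²)(1 + 1/56)] = 1.0093 × √(1 − r²).

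| Assumed r | √(1 − r²) | Width ratio | Change in 95% CI width |
|---|---|---|---|
| 0 | 1.000 | 1.009 | 0.9% wider |
| 0.3 | 0.954 | 0.963 | 3.7% narrower |
| 0.5 | 0.866 | 0.874 | 12.6% narrower |
| 0.7 | 0.714 | 0.721 | 27.9% narrower |

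Break-even is where 1 − r² = 1/1.0093², which gives r of about 0.135.

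**Step 2: what r might two weeks give?** This is a simulation on assumed inputs: 13 unobserved run-in days, 90 follow-up days, mean adherence 70%, SD 25 points, and a person-level correlation of 0.6 between the two periods.

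| Day-to-day autocorrelation of dosing | r | CI half-width, unadjusted to adjusted (points) |
|---|---|---|
| 0 (independent days) | 0.52 | 13.1 to 11.3 |
| 0.5 | 0.45 | 13.4 to 12.1 |
| 0.8 | 0.35 | 14.3 to 13.5 |

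Near ceiling (mean 90%, SD 5 points) r falls to between 0.05 and 0.35. By the Step 1 formula, that runs from 0.8% wider to about 5% narrower.

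**Step 3: chance imbalance.** The standard error of the difference in run-in means is √(2/30) = 0.258 SD. The chance of an imbalance above 0.25 SD is 33%, and above 0.5 SD it is 5%. An unadjusted estimate carries r times that imbalance. This is part of its sampling variation, not bias.

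**Step 4: validity.** In 5,000 simulated null trials under the Step 2 assumptions, the mean adjusted difference stayed within 0.13 points of zero and type I error was 4.3 to 5.5%.

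**Step 5: the covariate must be fixed before allocation.** The Study Visit 2 text lists randomisation before the review and reconciliation of the run-in record. If edits to run-in days differ by arm, the adjusted estimate shifts by the covariate slope times that difference. With slopes of 0.39 to 0.49 (from the simulation), a 5-point arm difference in edits moves the estimate by 0.39 × 5 = 1.95 to 0.49 × 5 = 2.45 points.

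**Step 6: outcome window.** Section VII does not say whether overall adherence includes the run-in. If 14 run-in days were pooled with 90 follow-up days, a true arm difference would shrink to 90/104 = 87% of its size.

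**The case against.** The strongest reply is that Section VII does not commit to an unadjusted analysis. It names no model at all, so adjustment is not ruled out, and the larger gap is the missing model, window and missing-data rule. That is fair: adjustment supplies none of these. But a plan that names no covariate leaves a useful choice open until after the data are seen.

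A second reply is that this is a pilot, with no decision rule tied to the width of the interval, and that the gain is unknown. That also stands, and it limits the weight of the point. The run-in may be atypical too: an observed first dose, check-in texts on days 2, 5 and 7, and some participants starting PrEP. If eligibility to continue (Drug Procurement) depended on run-in adherence, r would fall further. The documents do not say that it does.

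Stronger readings are tempting. A reader might infer that the unadjusted comparison is biased. It is not: allocation is random. A reader might infer that adjustment always narrows the interval and can never bias it. Steps 1 and 5 show otherwise: below r of about 0.135 the interval widens slightly, and edits made with the arm known could bias the adjusted estimate. A reader might also conclude that the intervention arm is exposed to messages for only 60/90 = 67% of follow-up. The documents do not establish this, because they disagree on when messages start. The conflict may be leftover visit numbering: the seven visits in Section VI fit Screening plus Visits 1 to 6, which makes Study Visit 2 the third. The contradictions about the window are separate items and add no weight to the case for adjustment.

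**Conclusion.** The point holds as a cheap improvement. Section VII leaves an available pre-randomisation measure of the outcome out of the arm comparison, and using it would probably tighten the estimate. The size cannot be fixed from the documents. For r between 0 and 0.7 it runs from 0.9% wider to about 28% narrower, with 30 per arm analysed. A gain of roughly 5 to 14% is plausible under the Step 2 assumptions, and little or nothing if adherence is near ceiling. The conclusion rests on the covariate being taken from the record as it stood before allocation.

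**What to change.** Add to Section VII, Aim 2:

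> For percent adherence and for weeks of adherence we will estimate the difference between randomised arms with a 95% confidence interval. Participants are analysed in the arm to which they were randomised, over post-randomisation device days only. Each comparison is adjusted for run-in percent adherence, defined as the percentage of days after the observed first dose and before randomisation with a detected ingestion, from the time-stamped device record as logged before allocation.

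Further details to settle:

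- Use the run-in record as edited after the Visit 2 reconciliation only in a sensitivity analysis.
- Define the denominator in days, as above. Up to 21 pills are supplied, so the run-in can exceed 14 days.
- Treat days coded −99 the same way in run-in and follow-up. Section XI gives only the code, so Section VII must first say whether such a day counts as missed or is left out.
- For weeks of adherence, use the same covariate with a method suited to a bounded count.

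Separately, reconcile the text that sets the outcome window:

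- **Message start.** The Intervention Condition text, the components table and Study Visit 1 tie LifeSteps or the message components to Visit 3. The Study Visit 2 procedures table lists LifeSteps counselling and programming at Visit 2.
- **Digital-pill period.** The Aim 2 and 3 introduction describes daily digital pills over 6 months. Drug Procurement supplies 90 after the run-in (90/182, about 49% of 6 months), Study Visit 5 has equipment returned, and Study Visit 6 lists only a dried blood spot and a questionnaire.

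The cost is wording, one export of the run-in record before allocation, and one degree of freedom. No new participants, visits or measurements are needed. The statistical downside is a widening of under 1% if r turns out low.
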